8.2.2 Exclusion Criteria

To be considered eligible for entry into the study, a subject must not meet any of the following exclusion criteria:

1. Any history of schizophrenia or schizoaffective disorder.

2. Any other current Axis I disorder, including, but not limited to, major depressive disorder, bipolar disorder, post-traumatic stress disorder, obsessive-compulsive disorder, premenstrual dysphoric disorder, and generalized anxiety disorder, which is in poor control and the primary focus of treatment.
3. A diagnosis of SAD.
4. A score >60 on the Liebowitz Social Anxiety Scale (LSAS).
5. Subjects who meet criteria for moderate or severe alcohol or substance use disorder within 1 year prior to study entry.
6. In the opinion of the Investigator, the subject has a significant risk for suicidal behavior during their participation in the study, or
 - a. At Screening (Visit 1): the subject scores “yes” on items 4 or 5 in the Suicidal Ideation section of the C-SSRS with reference to a 6-month period prior to screening; or
 - b. At Screening (Visit 1): the subject has had one or more suicidal attempts with reference to a 2 year period prior to screening; or
 - c. At Baseline (Visit 2): the subject scores “yes” on items 4 or 5 in the Suicidal Ideation section of the C-SSRS with reference to screening; or
 - d. The subject is considered to be an imminent danger to themselves or others.
7. Clinically significant nasal pathology or history of significant nasal trauma, nasal surgery, total anosmia, or nasal septum perforation that may have damaged the nasal chemosensory epithelium.
8. An acute or chronic condition, including an infectious illness, uncontrolled seasonal allergies at the time of the study, or significant nasal congestion that potentially could affect drug delivery to the nasal chemosensory epithelium. The Investigator may allow concomitant use of over-the-counter nasal decongestants as needed, since there is no apparent drug interaction between these and PH94B.
9. Concomitant use of any anxiolytics, such as benzodiazepines, buspirone, or cannabinoids during the study and within 30 days of Baseline (Visit 2).

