6.1. Statistical Definitions and Algorithms

6.1.1. Baseline

Baseline for each study assessment (where applicable) is defined in Table 2.

Table 2: Baseline Definitions

Parameters	Baseline
Safety parameters including physical examinations and ECGs.	The last non-missing assessment before the first dose of study drug. This assessment will be at Visit 1 (Screening).
Safety parameters including vital signs, clinical laboratory tests, MADRS, and C-SSRS.	The last non-missing assessment before the first dose of study drug at Visit 2 (Baseline).
Efficacy parameters including HAM-A total score, ADNLM total score, and IADQ total score.	The last non-missing assessment before the first dose of study drug at Visit 2 (Baseline).

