6.1.7.9. Columbia-Suicide Severity Rating Scale (C-SSRS)

The C-SSRS is a semi-structured interview that captures the occurrence, severity, and frequency of suicide-related thoughts and behaviors during the assessment period. The interview includes definitions and suggested questions to solicit the type of information needed to determine if a suicide-related thought or behavior has occurred. The C-SSRS has a “baseline” version, which will be completed at Visit 1 (Screening), and a “since last visit” version that will be completed at all subsequent visits.

There are a maximum of 19 items to be completed: 7 that are required, 10 potential additional items if there is a positive response to a required item, and 2 items for suicide/suicide behavior present during the interview. The C-SSRS uses dichotomous scales (i.e., yes or no), Likert scales, and text or narrative are used to further describe the thoughts or behaviors.

Subjects are considered to have had suicidal ideation during a time period (lifetime, last 6 months, since last visit) if they respond “Yes” to any of the 5 suicidal ideation questions listed below for that time period:

- Wish to be dead (Category 1)
- Non-specific active suicidal thoughts (Category 2)
- Active suicidal ideation with any methods (Category 3)
- Active suicidal ideation with some intent to act, without specific plan (Category 4)
- Active suicidal ideation with specific plan and intent (Category 5)

Subjects are considered to have had suicidal behavior during a time period if they respond “Yes” to any of the 5 suicidal behavior questions listed below for that time period:

- Completed suicide
- Actual attempt

- Interrupted attempt
- Aborted attempt
- Preparatory acts or behavior

Subjects are considered to have suicidal ideation or behavior during a time period if they responded “Yes” to any of the suicidal ideation or behavior questions for that time period.

A subject’s maximum suicidal ideation score is the maximum suicidal ideation category to which they responded “Yes”. Subjects are considered to have treatment emergent suicidal ideation if their maximum suicidal ideation score increased from a previous visit to the next visit after treatment with study drug.

Subjects are considered to have treatment emergent suicidal behavior if they did not have suicidal behavior prior to treatment with study drug but did have suicidal behavior at any visit after treatment with study drug.

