Aborted Attempt	XX (XX.X%)	XX (XX.X%)	XX (XX.X%)
Preparatory Acts or Behavior	XX (XX.X%)	XX (XX.X%)	XX (XX.X%)
Suicidal Ideation or Behavior			
Subject Engaged in Non-Suicidal Self-Injurious Behavior	XX (XX.X%)	XX (XX.X%)	XX (XX.X%)

Abbreviation: C-SSRS = Columbia Suicide Severity Rating Scale.

Note: Percentages are n/Number of subjects in the Safety population within treatment received and overall subjects * 100. The number and percent of subjects who experience the event at least once during treatment are summarized. Subjects were counted once for each C-SSRS section and once for each C-SSRS item answered "Yes" during treatment period. "Baseline/Screening" version was used for Visit 1 (Screening) and "Since Last Visit" was used for all other visits.

[1] Visit 6 (End of Treatment/Early Termination) includes data from subjects who either completed Visit 6 (End of Treatment) or who discontinued from the study and completed an early termination visit.

[2] Subjects are considered to have treatment emergent suicidal ideation if their maximum suicidal ideation score increased from a previous visit to the next visit after treatment with study drug.

[3] Subjects are considered to have treatment emergent suicidal behavior if they did not have suicidal behavior prior to treatment with study drug but did have suicidal behavior at any visit after treatment with study drug.

Reference Listings: 16.2.9.5

Programming Note: Display summaries for all visits, including Visit 1 (Screening), Visit 2 (Baseline), Visit 3, Visit 4, Visit 5, Visit 6 (End of Treatment/Early Termination), Visit 7 (Follow-Up). Present treatment emergent counts and percentages as the last lines in the table after Visit 7 (Follow-Up).

[figure not shown]

Table 14.3.6.4 (cont.)
Summary of Columbia Suicide Severity Rating Scale (C-SSRS) by Visit
Safety Population

Study Visit [1] C-SSRS Section C-SSRS Item / Statistic	PH94B (N=XX)	Placebo (N=XX)	Overall (N=XX)
Visit 2 (Baseline)			
Suicidal Ideation: Since Last Visit	XX (XX.X%)	XX (XX.X%)	XX (XX.X%)
Wish to be Dead	XX (XX.X%)	XX (XX.X%)	XX (XX.X%)
Non-Specific Active Suicidal Thoughts	XX (XX.X%)	XX (XX.X%)	XX (XX.X%)
Active Suicidal Ideation with Any Methods	XX (XX.X%)	XX (XX.X%)	XX (XX.X%)
Active Suicidal Ideation with Some Intent	XX (XX.X%)	XX (XX.X%)	XX (XX.X%)
Active Suicidal Ideation with Specific Plan	XX (XX.X%)	XX (XX.X%)	XX (XX.X%)
Suicidal Behavior: Since Last Visit	XX (XX.X%)	XX (XX.X%)	XX (XX.X%)

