Suicidal Behavior: Since Last Visit	XX (XX.X%)	XX (XX.X%)	XX (XX.X%)
Completed Suicide	XX (XX.X%)	XX (XX.X%)	XX (XX.X%)
Actual Attempt	XX (XX.X%)	XX (XX.X%)	XX (XX.X%)
Interrupted Attempt	XX (XX.X%)	XX (XX.X%)	XX (XX.X%)
Aborted Attempt	XX (XX.X%)	XX (XX.X%)	XX (XX.X%)
Preparatory Acts or Behavior	XX (XX.X%)	XX (XX.X%)	XX (XX.X%)
Suicidal Ideation or Behavior	XX (XX.X%)	XX (XX.X%)	XX (XX.X%)
Subject Engaged in Non-Suicidal Self-Injurious Behavior	XX (XX.X%)	XX (XX.X%)	XX (XX.X%)
Treatment Emergent Suicidal Ideation [2]	XX (XX.X%)	XX (XX.X%)	XX (XX.X%)
Treatment Emergent Suicidal Behavior [3]	XX (XX.X%)	XX (XX.X%)	XX (XX.X%)
Treatment Emergent Suicidal Ideation or Behavior	XX (XX.X%)	XX (XX.X%)	XX (XX.X%)

Abbreviation: C-SSRS = Columbia Suicide Severity Rating Scale.

Note: Percentages are n/Number of subjects in the Safety population within treatment received and overall subjects * 100. The number and percent of subjects who experience the event at least once are summarized. Subjects were counted once for each C-SSRS section and once for each C-SSRS item answered "Yes" during treatment period. "Baseline/Screening" version was used for Visit 1 (Screening) and "Since Last Visit" was used for all other visits.

[1] Visit 6 (End of Treatment/Early Termination) includes data from subjects who either completed Visit 6 (End of Treatment) or who discontinued from the study and completed an early termination visit.

[2] Subjects are considered to have treatment emergent suicidal ideation if their maximum suicidal ideation score increased from a previous visit to the next visit after treatment with study drug.

[3] Subjects are considered to have treatment emergent suicidal behavior if they did not have suicidal behavior prior to treatment with study drug but did have suicidal behavior at any visit after treatment with study drug.

Reference Listings: 16.2.9.5

Programming Note: Display summaries for all visits, including Visit 1 (Screening), Visit 2 (Baseline), Visit 3, Visit 4, Visit 5, Visit 6 (End of Treatment/Early Termination), Visit 7 (Follow-Up). Present treatment emergent counts and percentages as the last lines in the table after Visit 7 (Follow-Up).

AD-ST-33.06 Effective date: 12-Nov-2020

[figure not shown]

Table 14.3.6.5
Summary of Montgomery-Asberg Depression Rating Scale (MADRS) Total Score by Visit
Safety Population

Study Visit [1] Statistic	PH94B (N=XX)		Placebo (N=XX)		Overall (N=XX)	
	Observed	CFB	Observed	CFB	Observed	CFB

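### Treatment-emergent suicidal ideation is defined by any visit-to-visit rise, so subjects with ideation at Visit 2 who improve and then partly or fully return are counted although they never exceed baseline

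*SAP*

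**What the plan says.** SAP 6.1.7.9 defines the ideation score: a subject's "maximum suicidal ideation score is the maximum suicidal ideation category to which they responded" Yes, on categories 1 to 5. It then gives the emergence rule: "Subjects are considered to have treatment emergent suicidal ideation if their maximum suicidal ideation score increased from a previous visit to the next visit" following study drug. Footnote [2] of the Table 14.3.6.4 shell carries the same condition, "if their maximum suicidal ideation score increased from a previous visit to the next visit after treatment with study drug", so this is what would be programmed. SAP 9.7 reports the resulting number and percentage by arm and overall, and adds no further condition.

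Three other places in the SAP use the pre-treatment state as the reference:

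- Table 2 (SAP 6.1.1) has a row for "Safety parameters including vital signs, clinical laboratory tests, MADRS, and C-SSRS", with baseline set as the last available assessment before first dose, at Visit 2.
- The behavior rule, in the same subsection, counts subjects who "did not have suicidal behavior prior to treatment with study drug but did have suicidal behavior at any visit after treatment".
- The adverse event rule (SAP 6.1.7.1) counts an event that began before treatment only if its severity or relationship increases.

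**The concern.** In a safety table, treatment emergent should mean new or worse than before treatment. The ideation rule compares each visit only with the one before it, so a rise from an improved level counts the same as a rise above baseline. The row for ideation or behavior then combines a component with no pre-treatment reference and one that has it.

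The situation can arise in this trial. Protocol 8.2.2 excludes at Visit 2 a subject answering yes to "items 4 or 5 in the Suicidal Ideation section of the C-SSRS with reference to screening". Categories 1 to 3 are not excluded by score, although investigator judgement of suicide risk also applies.

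At stake is the meaning of a descriptive count on suicidality. Protocol synopsis: 40 subjects randomized 1:1, so about 20 per arm, and one such flag moves an arm's percentage by about 1/20 = 5 points.

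**Working it through.** The plan states no figure on this point, so there is none to reproduce. The check compares two rules on the same score paths.

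**Inputs**
- Score 0 to 5; a subject with no Yes is taken as 0 (SAP 6.1.7.9).
- Visit 2 score b from 0 to 3 (Protocol 8.2.2).
- Five post-dose assessments, Visits 3 to 7. The shell note says "Display summaries for all visits, including Visit 1 (Screening), Visit 2 (Baseline), Visit 3, Visit 4, Visit 5" and goes on to Visits 6 and 7.
- A missed visit is assumed to be bridged by the last available one.

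**Rules**
- SAP rule: flag if any score exceeds the preceding one, over Visits 2 to 7.
- Baseline rule: flag if the maximum over Visits 3 to 7 exceeds b.

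**Step 1. Single paths**

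| Visit 2 | Visits 3-7 | SAP rule | Baseline rule |
|---|---|---|---|
| 2 | 1, 0, 1, 2, 2 | flag | no flag |
| 2 | 0, 0, 0, 0, 1 | flag | no flag |
| 1 | 0, 1, 0, 0, 0 | flag | no flag |
| 2 | 3, 2, 2, 2, 2 | flag | flag |
| 3 | 3, 3, 3, 3, 3 | no flag | no flag |
| 1 | 0, 0, 0, 0, 0 | no flag | no flag |

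The second path rises only at Visit 7, after the one-week washout, and still ends below baseline.

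**Step 2. Which never-above-baseline paths are flagged.** There are (b+1)^5 paths that stay at or below b. The SAP rule spares only those that never rise, and there are C(5+b, b) of these.

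| b | Paths at or below b | Never rising | Flagged by SAP rule only |
|---|---|---|---|
| 0 | 1 | 1 | 0 |
| 1 | 32 | 6 | 26 |
| 2 | 243 | 21 | 222 |
| 3 | 1,024 | 56 | 968 |

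These are counts of possible paths, not probabilities.

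**Step 3. What the SAP rule misses.** If any post-dose score exceeds b, there must be a rise somewhere between Visit 2 and that visit, so the SAP rule flags it too. Enumeration of all 6^5 = 7,776 paths at each b agrees: none is flagged by the baseline rule but not by the SAP rule.

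**Step 4. Illustration with assumed probabilities.** Take b = 1, with a score of 1 with probability p and otherwise 0, independently at each of five visits. The SAP rule spares only the six sequences of k ones followed by 5-k zeros, so

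P(flag) = 1 - sum over k = 0 to 5 of p^k (1-p)^(5-k).

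- p = 0.1: 1 - (0.59049 + 0.06561 + 0.00729 + 0.00081 + 0.00009 + 0.00001) = 1 - 0.6643 = 0.336. By symmetry p = 0.9 gives the same.
- p = 0.3 or 0.7: 0.708.
- p = 0.5: 1 - 6/32 = 0.812.

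Under the baseline rule the probability is 0 throughout.

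**The case against.** The strongest defence is that this is a sensitive screen in a descriptive table. By step 3 no rise above the Visit 2 score is lost. Table 14.3.6.4 shows each category at each visit by arm, and Listing 16.2.9.5 gives every subject's answers, so a reader can check whether a flag exceeded baseline. Ideation returning at Visit 7 is worth showing, since that visit also looks for withdrawal effects. The group at risk may be small or empty: entry requires a MADRS total below 20, and subjects judged at significant suicide risk are excluded. All of this stands, and it keeps the point minor. It does not justify the label, because the plan already reports return of ideation by visit and elsewhere uses treatment emergent relative to the pre-treatment state.

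A reader might infer more than the documents support:

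- *That everyone who stays at or below baseline is flagged.* Flat or steadily falling subjects are not, and at a Visit 2 score of 0 the two rules agree exactly.
- *That the rule hides a true safety signal.* It adds flags and removes none. The cost is specificity.
- *That it is biased against PH94B.* A spurious flag does require an earlier fall, so the arm that improves more could collect more of them. But the illustration has no treatment effect, and nothing in the documents gives a size.

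One could also read the rule as comparing only the last pre-dose visit with the first post-dose visit. That would avoid the over-count but miss emergence after Visit 3, and nothing in the SAP supports it.

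**Conclusion.** The definition is wrong as written, though minor. It labels as treatment emergent a subject whose ideation fell on treatment and only partly or fully returned, and no other section corrects this. The error is confined to subjects with a Visit 2 score of 1 to 3 who first fall and then rise.

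The effect on the reported percentages cannot be calculated, because the documents do not give the number of such subjects. The 34% to 81% is a per-subject probability within that group. It rests on baseline 1, scores limited to 0 or 1, independence between visits and p from 0.1 to 0.9. It illustrates the mechanism and does not forecast a rate.

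**What to change.** In SAP 6.1.7.9 and in footnote [2] of Table 14.3.6.4, define treatment-emergent suicidal ideation as a maximum ideation category at any post-dose visit (Visits 3 to 7) greater than the category at the Table 2 baseline, meaning the Visit 2 since-last-visit assessment.

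Do not fold the Screening six-month look-back into the reference. A subject at category 3 in the six months before Screening, 0 at Visit 2 and 3 on treatment would then go unflagged, which would mask re-emergence on treatment. The Visit 2 window is itself somewhat wider than the weekly post-dose windows, since screening lasts 7 to 35 days, but it is the baseline the SAP already names.

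The cost is two text edits before unblinding. The only downside is fewer flags; every by-visit response remains in the table and listing.

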6.1.7.10. Physician Withdrawal Checklist (PWC-20)

The PWC-20 is a 20-item simple instrument for assessing anxiolytic discontinuation symptoms. It consists of 20 questions related to withdrawal from benzodiazepines or other anti-anxiety compounds rated on a 4-point scale (0=“Not Present”, 1=“Mild”, 2=“Moderate”, 3=“Severe”). The symptoms measured are based on those that are potentially related to anxiolytic withdrawal: gastrointestinal, mood, sleep, motor, somatic, perception and cognition. The questions will cover any symptoms that might occur during the week following discontinuation of PH94B.

The PWC-20 total score will be calculated as the sum of the 20 items and will range from 0 to 60.

Subjects with any score >0 will be categorized as having a withdrawal symptom. The proportion of subjects with withdrawal symptoms will be calculated as the number of subjects with any score >0 divided by the total number of subjects in the population of interest.

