10.2.5 Follow-up (Visit 7)

At Visit 7, the following assessments will be completed:

- Administer HAM-A
- Administer C-SSRS (since last visit)
- Administer PWC-20
- Measure vital signs after the subject has rested for 5 minutes: seated systolic and diastolic blood pressure, heart rate, respiratory rate, body temperature, and ECG

- Record concomitant medication use
- Review and record AEs

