When the subject returns for Visit 6 (End of Treatment), besides the assessments completed at Visits 3 through 5, the subjects will also complete the MADRS, ADNM, and IADQ; and have a physical examination, ECG, blood tests and urinalysis, urine drug screen, and urine pregnancy test (if appropriate). Any remaining IP vials will be collected.

The subject will then come back after a one-week washout period for Visit 7 (Follow-up). During this visit, AEs concomitant medications since the last visit, and vital signs will be collected. In addition, the HAM-A, C-SSRS, and 20-item Physician Withdrawal Checklist (PWC-20) will be administered.

Subjects who discontinue prior to Visit 6 (End of Treatment), will undergo a Visit 6 (Early Termination) visit, and provide all Visit 6 outcome measures and safety assessments for the efficacy analysis.

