4.2. Interim Analysis and Data Monitoring

No interim analyses or data monitoring are planned.

5. Analysis Populations

The following analysis populations are planned for this study:

- **All Subjects Population:** All subjects who sign an informed consent, participate in a Visit 1 (Screening), and are entered into the eCRF will be included in the All Subjects

population. The All Subjects population will be used for summaries of subject disposition.

- **Safety Population:** The Safety population includes all subjects who are dispensed IP and reported administering at least 1 dose of IP. The Safety population will be used for safety analyses. For analyses of the Safety population, each subject will be analyzed by the actual treatment received, even if it differs from the subject's randomized treatment assignment.
- **Intent-to-Treat (ITT) Population:** The ITT population includes all subjects who are randomized and have one documented dose of IP at Visit 2 (Baseline). The ITT population will be used for efficacy analyses. For analyses of the ITT population, each subject will be analyzed by their randomized treatment assignment, even if the subject did not receive the assigned treatment or did not follow the protocol until completion.

Assignment of subjects to populations will be confirmed at a blinded data review meeting to be held before the study database is locked. All protocol deviations that occur during the study will be considered for their severity/impact and will be taken into consideration when subjects are assigned to analysis populations.

6. General Issues for Statistical Analysis

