6.1.7.3. Clinician’s Global Impression – Improvement (CGI-I) Scale

The CGI scale is a clinician-rated scale assessment of the clinician’s view of the subject’s global health prior to and after participation in a clinical study. The improvement component (CGI-I) asks the clinician to respond to the following question:

“Rate total improvement whether or not, in your judgement, it is due entirely to drug treatment. Compared to his condition at admission to the project, how much has he changed?”

The rating is on an 8-point scale (0=“Not assessed”, 1=“Very much improved”, 2=“Much improved”, 3=“Minimally Improved”, 4=“No change”, 5=“Minimally worse”, 6=“Much worse”, 7=“Very much worse”).

Subjects with scores of 1 (Very much improved) or 2 (Much improved) at the end of treatment with PH94B will be categorized as “responders”. The proportion of CGI-I responders will be calculated as the number of CGI-I responders divided by the number of subjects with non-missing CGI-I scores in the population of interest.

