8.3. Exploratory Efficacy Analysis

To evaluate the efficacy of PH94B over time, observed values and changes from baseline in HAM-A total scores will be summarized by visit and by treatment group. Summaries of CGI-I and PGI-C scores by visit and by treatment group will be displayed with the secondary efficacy analyses.

The differences in changes from baseline between the PH94B and placebo groups in HAM-A total scores at Visits 3, 4, and 5 will be assessed using the ANCOVA analysis described in Section 8.1 for the observed data.

The ADNM and IADQ observed subscores and changes from baseline will be displayed in by-subject listings.

9. Safety and Tolerability Analysis

Safety in this study will be evaluated based on data collected on AEs, clinical laboratory assessments, vital signs, 12-lead ECGs, and physical examinations including examination of the nasal passages, C-SSRS, MADRS scores, and PWC-20 scores.

All safety analysis reporting will be based on the Safety population (as defined in Section 5).

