Abbreviations: CI = confidence interval; PWC-20 = Physician Withdrawal Checklist; SD = standard deviation; SE = standard error.
 Note: Percentages are n/Number of subjects in the Safety population within treatment received and overall subjects * 100. The PWC-20 is a 20-item instrument for assessing anxiolytic discontinuation symptoms. Subjects with any score >0 were categorized as having a withdrawal symptom. The proportion of subjects with withdrawal symptoms was calculated as the number of subjects with any score >0 divided by the total number of subjects in the population of interest.
 [1] P value was obtained from a two-sample t-test comparing PWC-20 total score in PH94B and Placebo treated subjects.
 Reference Listing: 16.2.9.8

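### The PWC-20 withdrawal percentages divide by every Safety subject, so anyone without a Visit 7 checklist is counted as symptom-free

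*SAP*

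**What the plan says.** SAP 6.1.7.10 sets the numerator: "Subjects with any score >0 will be categorized as having a withdrawal symptom". The denominator is the numerator's whole population: the count is "divided by the total number of subjects in the population of interest". Section 9 of the SAP makes the Safety population the basis of all safety reporting, and Section 5 defines it by dosing alone: "The Safety population includes all subjects who are dispensed IP and reported administering at least 1 dose of IP". Attending Visit 7 is not required.

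The Table 14.3.6.6 footnote repeats the definition and adds a rule that also governs the individual symptom rows: "Percentages are n/Number of subjects in the Safety population within treatment received and overall subjects * 100".

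The checklist is given once. Protocol 10.2.5 lists it for the follow-up visit ("Administer PWC-20"), and SAP 3.2 places it at the same visit: "In addition, the HAM-A, C-SSRS, and 20-item Physician Withdrawal Checklist (PWC-20) will be administered". The Visit 6 list in Protocol 10.2.4 does not contain it. Under Protocol 8.3 and SAP 3.2, that list is what is collected from a subject who stops early and does not keep to the schedule.

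Three other statements bear on the point. SAP 6.1.4 says that safety data are not imputed and are taken as they were recorded. SAP 9.9 compares mean PWC-20 total scores by a two-sample t-test. For the CGI-I, SAP 6.1.7.3 uses a different base: responders are "divided by the number of subjects with non-missing CGI-I scores in the population of interest".

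**The concern.** A percentage should be taken over the subjects in whom the event could have been recorded. For adverse events, which are collected from everyone dosed, the full Safety population is a natural base. The PWC-20 is a single checklist completed about a week after treatment ends, and a subject who never completed it contributes no information on withdrawal symptoms. Leaving that subject in the denominator has the arithmetic effect of imputing absence of symptoms. SAP 6.1.4 says safety data will not be imputed.

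It also puts one table on two bases. In Table 14.3.6.6 the total-score n, mean, difference and t-test can use only subjects with a score, while the percentages above them use everyone.

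At stake is the symptom rate from the study's dedicated withdrawal instrument. According to the protocol synopsis, earlier human exposure was under two weeks and at fewer than four doses a day, so this trial's withdrawal data are new. An understated rate, or a between-arm gap that only reflects attendance at Visit 7, would be a poor basis for planning later studies.

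**Working it through.** The documents state no PWC-20 rate and no missed-visit rate, so there is no figure of theirs to reproduce. The steps below use direct arithmetic.

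**Inputs.** N = 20 per arm, from 40 subjects randomized 1:1 (protocol synopsis), assuming all are dosed. m = Safety subjects in an arm with no PWC-20 (assumed). x = subjects with any score above zero (assumed).

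**Formulas.**
- Planned rate = x / N.
- Assessed rate = x / (N − m).
- So planned rate = assessed rate × (1 − m/N), and the understatement is assessed rate × m/N.
- Depending on the unseen outcomes, the full-population rate lies between x/N and (x + m)/N. The planned rule always prints x/N, the floor.

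**Single-arm example.** x = 8, N = 20, m = 4. Planned: 8/20 = 40%. Assessed: 8/16 = 50%. Bounds: 8/20 = 40% to (8 + 4)/20 = 60%.

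**Understatement in percentage points, N = 20:**

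| m | assessed rate 25% | 50% | 75% |
|---|---|---|---|
| 0 | 0 | 0 | 0 |
| 1 | 1.25 | 2.5 | 3.75 |
| 2 | 2.5 | 5.0 | 7.5 |
| 4 | 5.0 | 10.0 | 15.0 |
| 6 | 7.5 | 15.0 | 22.5 |

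**Between arms (assumed counts).**
- Equal assessed rates of 50%, 4 missing on PH94B and none on placebo: 8/20 = 40% against 10/20 = 50%, an apparent difference of −10 points where the assessed difference is 8/16 − 10/20 = 0.
- The same counts with the arms exchanged: an apparent +10 points, against PH94B.
- A difference hidden: 12/16 = 75% on PH94B against 12/20 = 60% on placebo is +15 points among those assessed, but prints as 12/20 against 12/20, a difference of 0.
- Equal assessed rates and equal m: both rates are understated by the same amount and no false difference appears.

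**The case against.** The strongest defence is that the rule follows the SAP's own convention. Section 4.1 makes the total study population the default denominator unless something else is specified, and other safety shells, such as the C-SSRS table, use the full Safety N. The contrast with CGI-I is also weaker than it looks. The text of 6.1.7.3 uses non-missing scores, but the CGI-I shell prints percentages on the ITT total, with a row for missing values. This stands. The inconsistency with CGI-I is not the main argument, and the convention explains the rule. It does not make the rule suitable for a once-only scale, and the PWC-20 shell lacks the missing row that the CGI-I shell has.

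Second, the missingness is not hidden. The total-score block of Table 14.3.6.6 has an n row in each column, which Section 4.1 defines as subjects with non-missing values, so a careful reader could rescale the percentages. That stands too. The printed rates are still on the wrong base, and nothing beside them says so.

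Third, the only PWC-20 test is the t-test on observed total scores, which the denominator does not touch. The PWC-20 is also not among the safety endpoints listed in Protocol 6.4 or SAP 2.2.2. This limits the weight of the point but does not remove it.

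Fourth, a reader might infer that every early discontinuer lacks a PWC-20. The documents do not say this. Protocol 8.3 first asks discontinuers to return for their scheduled assessments, and the Visit 6 list is the fallback, so some will have a score. The schedule-of-events table is not in the text available, so timing was checked against the visit descriptions only.

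**Conclusion.** The point holds. The rule is stated, not merely left open. In any arm where some Safety subjects have no PWC-20 and at least one assessed subject has a symptom, it understates the rate by the assessed rate times m/N. At N = 20 and an assessed rate of 50%, each missing checklist costs 2.5 percentage points. If everyone attends Visit 7, the two denominators agree.

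A reader might go further and conclude that the rule makes PH94B look safer on stopping than it is. The documents do not support that. They give no missed-visit counts by arm. The earlier experience in Protocol 5.2.2 and 5.3 reports no early terminations for adverse events in the two Phase 2 social anxiety studies and no listed effect in more PH94B than placebo subjects. More dropout on placebo would tilt the comparison against PH94B. Only the downward shift within an arm is certain in direction. All counts and rates in the working are assumptions.

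This is a worthwhile correction to a descriptive safety summary, and it does not affect the primary analysis.

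**What to change.** In SAP 6.1.7.10, and in the footnote to Table 14.3.6.6, define the denominator as Safety subjects with a non-missing PWC-20, both for the overall proportion and for each symptom row. Add a row to the shell that counts Safety subjects with a missing PWC-20, by arm and overall. The assessed n already appears under the total score; repeating it above the symptom rows would make the base plain.

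The cost is one sentence, one footnote and one table row, with no new data collection. The drawback is that the assessed-only rate can still be biased if missing Visit 7 is related to symptoms. The change does not cure that, which is why the missing count must stand beside the percentages.
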